### **7.3. Body Weight, Body Mass Index and Vital Signs**

Descriptive statistics will be provided by treatment group for vital signs as follows:

- Baseline value
- Values at each postbaseline visit
- Change from baseline at each postbaseline visit

A baseline value will be defined as the last available value collected on or prior to the date/time of first dose of study drug. Change from baseline to a postbaseline visit will be defined as the postbaseline value minus the baseline value.

In the case of multiple values in an analysis window, data will be selected for analysis as described in Section 3.8.3. No formal statistical testing is planned.

A by-subject listing of vital signs will be provided by subject ID number and time point in chronological order. A listing of body weight and BMI will be provided separately.

### **7.4. Prior and Concomitant Medications**

Medications collected at screening and during the study will be coded using the current version of the World Health Organization (WHO) Drug dictionary.

#### **7.4.1. Prior Medications**

Prior medications are defined as any medications taken before a subject took the first study drug. Only prior HBV medications will be summarized. A by-subject listing of prior HBV medications will also be provided.

Prior HBV medications will be summarized by preferred name using the number and percentage of subjects by treatment group. A subject reporting the same medication more than once will be counted only once when calculating the number and percentage of subjects who received that medication. The summary will be ordered by preferred name in order of descending overall frequency. For drugs with the same frequency, sorting will be done alphabetically.

For the purposes of analysis, any medication with a start date prior to the first dosing date of study drug will be included in the prior medication summary regardless of when the stop date is. If a partial start date is entered the medication will be considered prior unless the month and year (if day is missing) or year (if day and month are missing) of the start date are after the first dosing date. Medications with a completely missing start date will be included in the prior medication summary, unless otherwise specified.

Summaries will be based on the Safety Analysis Set. No formal statistical testing is planned.

#### **7.4.2. Concomitant Medications**

Concomitant medications are defined as medications taken while a subject took study drug. Use of concomitant medications will be summarized by preferred name using the number and percentage of subjects by treatment group. A subject reporting the same medication more than once will be counted only once when calculating the number and percentage of subjects who received that medication. The summary will be ordered by preferred name in descending overall frequency. For drugs with the same frequency, sorting will be done alphabetically.

For the purposes of analysis, any medications with a start date prior to or on the first dosing date of study drug and continued to be taken after the first dosing date, or started after the first dosing date but prior to or on the last dosing date of study drug will be considered concomitant medications. Medications started and stopped on the same day as the first dosing date or the last dosing date of study drug will also be considered concomitant. Medications with a stop date prior to the date of first dosing date of study drug or a start date after the last dosing date of study drug will be excluded from the concomitant medication summary. If a partial stop date is entered, any medication with the month and year (if day is missing) or year (if day and month are missing) prior to the date of first study drug administration will be excluded from the concomitant medication summary. If a partial start date is entered, any medication with the month and year (if day is missing) or year (if day and month are missing) after the study drug stop date will be excluded from the concomitant medication summary. Medications with completely missing start and stop dates will be included in the concomitant medication summary, unless otherwise specified.

Summaries will be based on the Safety Analysis Set. No formal statistical testing is planned.

All prior and concomitant medications (other than per-protocol study drugs) will be provided in a by-subject listing sorted by subject ID number and administration date in chronological order.

## **7.5. Electrocardiogram Results**

ECG analysis results are intended to identify meaningful abnormalities. If potential abnormalities of interest are identified, further analyses may be conducted.

A shift table of the investigators' assessment of ECG results at Week 12 compared with baseline values will be presented by treatment group using the following categories: normal; abnormal, not clinically significant; abnormal, clinically significant; or missing. The number and percentage of subjects in each cross-classification group of the shift table will be presented. Subjects with a missing value at baseline or postbaseline will not be included in the denominator for percentage calculation. No formal statistical testing is planned.

A by-subject listing for ECG assessment results will be provided by subject ID number and visit in chronological order.

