### **6.8.3. Electrocardiogram Assessment**

Subjects should rest quietly in the supine position for a minimum of 5 minutes prior to each scheduled ECG acquisition and should remain in that position until the recording is complete. There should be no environmental distractions (including TV, radio, video games, and conversation) while the subjects are resting prior to and during the recordings.

Electrocardiograms will be recorded using the site's standard ECG equipment. All ECGs will be obtained using instruments that analyze data using the same algorithms and produce the same data for interpretation. Electrode placement will be performed according to the method of Wilson, Goldberger, and Einthoven with a check to confirm that the aVR lead is not inverted.

The investigator or other qualified individuals at the study center will review ECGs to assess for changes in ECG intervals and morphology as compared with pretreatment ECGs. ECG interval measurements output by the machine will be used for bedside safety monitoring.

Collection of additional ECGs for routine safety monitoring at additional time points or days is at the discretion of the investigator based on GCP.

QTc interval will be reported using Fridericia's correction:  $QTcF = QT/RR^{0.33}$

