### **7.5. Clinical Laboratory Abnormalities and Other Abnormal Assessments as Adverse Events or Serious Adverse Events and Toxicity Management**

Laboratory abnormalities are usually not recorded as AEs or SAEs. However, laboratory abnormalities (e.g., clinical chemistry, hematology, and urinalysis) independent of the underlying medical condition that require medical or surgical intervention or lead to investigational medicinal product interruption or discontinuation must be recorded as an AE, as well as an SAE, if applicable. In addition, laboratory or other abnormal assessments (e.g., ECG, X-rays, and vital signs) that are associated with signs and/or symptoms must be recorded as an AE or SAE if they meet the definition of an AE (or SAE) as described in Sections 7.1.1 and 7.1.2. If the laboratory abnormality is part of a syndrome, record the syndrome or diagnosis (i.e., anemia) not the laboratory result (i.e., decreased hemoglobin).

Severity should be recorded and graded according to the GSI Grading Scale for Severity of Adverse Events and Laboratory Abnormalities ([Appendix 3](#)). For AEs associated with laboratory abnormalities, the event should be graded on the basis of the clinical severity in the context of the underlying conditions; this may or may not be in agreement with the grading of the laboratory abnormality.

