Hypertension (with repeat testing at same visit)	140–159 mmHg systolic OR 90–99 mmHg diastolic	> 159–179 mmHg systolic OR > 99–109 mmHg diastolic	> 179 mmHg systolic OR > 109 mmHg diastolic	Life-threatening consequences (e.g., malignant hypertension) OR Hospitalization (other than ER visit) indicated
Pediatric ≤ 17 Years (with repeat testing at same visit)	NA	91st–94th percentile adjusted for age, height, and gender (systolic and/or diastolic)	≥ 95th percentile adjusted for age, height, and gender (systolic and/or diastolic)	Life-threatening consequences (e.g., malignant hypertension) OR Hospitalization indicated (other than emergency room visit)
Hypotension	NA	Symptomatic, corrected with oral fluid replacement	Symptomatic, IV fluids indicated	Shock requiring use of vasopressors or mechanical assistance to maintain blood pressure
Pericardial Effusion	Asymptomatic, small effusion requiring no intervention	Asymptomatic, moderate or larger effusion requiring no intervention	Effusion with non-life-threatening physiologic consequences OR Effusion with nonurgent intervention indicated	Life-threatening consequences (e.g., tamponade) OR Urgent intervention indicated

CARDIOVASCULAR				
	Grade 1	Grade 2	Grade 3	Grade 4
Prolonged PR Interval	PR interval 0.21 to 0.25 sec	PR interval > 0.25 sec	Type II 2nd degree AV block OR Ventricular pause > 3.0 sec	Complete AV block
Pediatric ≤ 16 Years	1st degree AV block (PR > normal for age and rate)	Type I 2nd degree AV block	Type II 2nd degree AV block	Complete AV block
Prolonged QTc	Asymptomatic, QTc interval 0.45 to 0.47 sec OR Increase interval < 0.03 sec above baseline	Asymptomatic, QTc interval 0.48 to 0.49 sec OR Increase in interval 0.03 to 0.05 sec above baseline	Asymptomatic, QTc interval ≥ 0.50 sec OR Increase in interval ≥ 0.06 sec above baseline	Life-threatening consequences, e.g., Torsade de pointes or other associated serious ventricular dysrhythmia
Pediatric ≤ 16 Years	Asymptomatic, QTc interval 0.450 to 0.464 sec	Asymptomatic, QTc interval 0.465 to 0.479 sec	Asymptomatic, QTc interval ≥ 0.480 sec	Life-threatening consequences, e.g., Torsade de pointes or other associated serious ventricular dysrhythmia

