**CCI**

- a. The Early Discontinuation (ED) visit should be performed within 14 days from notification of study discontinuation.
- b. Symptom directed physical exam will only be performed when subject is experiencing symptoms.
- c. To completed at Treatment Free Follow up Week 4 only: AE review, complete physical examination, and urine pregnancy test.
- d. Vital signs include blood pressure, pulse, respiration rate and temperature.
- e. QTc interval will be reported using Fridericia’s correction: QTcF QT/RR0333. Subjects must rest quietly in the supine position for a minimum of 5 minutes prior to the recording.
- f. For female subjects of childbearing potential, the serum pregnancy test will be performed at Screening. Urine test will be performed at all other visits as indicated. Positive urine test will be confirmed with serum test. Pregnancy testing should include prevention counseling.
- g. Qualitative HBV serology: (HBeAg [reflex HBeAb if HBeAg is negative] and HBsAg [reflex HBsAb if HBsAg is negative]). Collected every 12 weeks during the study. Post Treatment visit Weeks 12 and 24.
- h. PBMCs to be collected at Weeks 4, 8, 12, and 24 only. PBMC sample collection is only required at the sites that have access to PBMC processing laboratory.
- i. Weeks 2 and 8 PK samples will be collected between 15 minutes and 4 hours post dose. **CCI**
- j. Single PK sample will be collected at any time on all other Post Day 1 visits **CCI**. For Group 4, single PK will be collected through Week 12 only.
- k. **CCI**
- l. In the event of a positive result and/or antigen testing for HIV, HDV, or HCV serology, reflex tests will automatically be performed.
- m. In clinic dose required for Weeks 2 and 8 single PK samples **CCI**
- n. **CCI**
- o. HBV genotyping for Groups 1 3 and 5 only, for Group 4 historic genotype should be documented in EDC if available.
- p. Serum sample collected will be used for HBV viral sequencing and possible phenotypic analyses for all groups or ddPCR for Group 4.

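### No QTcF summary is pre-specified: the only ECG table is a shift of the investigators' normal/abnormal call, so asymptomatic QTc prolongation is tabulated as such only by discretion

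*SAP*

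**What the plan says.** SAP 7.5 gives one ECG summary. The investigators' "assessment of ECG results at Week 12 compared with baseline values will be presented by treatment group using the following categories", which are normal, abnormal not clinically significant, abnormal clinically significant, and missing. It adds that "If potential abnormalities of interest are identified, further analyses may be conducted", without a trigger or content, and that "A by-subject listing for ECG assessment results will be provided by subject ID number and visit in chronological order". It plans no descriptive statistics, change from baseline or threshold counts for QTcF or any other interval. The only other mention of QTcF in the SAP is footnote e to the schedule in Appendix 1: "QTc interval will be reported using Fridericia"'s correction.

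The protocol treats QTcF as a number. It is an inclusion criterion with sex-specific limits (4.2, 4.4). Section 6.8.3 states that "QTc interval will be reported using" Fridericia's correction, asks the reviewer of each tracing to look at interval changes against pretreatment, and says that "ECG interval measurements output by the machine will be used for bedside safety monitoring". Appendix 3 grades prolonged QTc by absolute value or by increase from baseline. Adult Grades 1 to 3 are all asymptomatic, and Grade 3 reads "Asymptomatic, QTc interval ≥ 0.50 sec OR Increase in interval ≥ 0.06 sec above baseline".

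**The concern.** Safety and tolerability of the 12-week regimens is a primary objective. The trial is open-label, and Group 5 takes 400 mg for 12 weeks, whereas protocol 1.4.1 describes 400 mg for 7 or 12 days and up to 200 mg for 12 weeks. The SAP gives vital signs and selected laboratory tests a baseline value, visit values and change from baseline (7.2.1, 7.3). For the ECG it keeps only a subjective three-level call made by unblinded sites and leaves out the measured interval.

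A rise in QTcF that does not lead the investigator to call the tracing abnormal leaves no mark in that table. If the call is abnormal, the table does not say why. The pre-specified output therefore cannot show a group's mean QTcF change, or how many subjects met the protocol's own QTc cut-offs.

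**Working it through.** The documents state no figure on this point, so the check has two parts: a trace of every route to a summary table, and an illustration with assumed values.

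**Routes for an asymptomatic rise in QTcF**

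1. *ECG shift table (SAP 7.5).* It shows the category only. The QTc finding is not identifiable.
2. *Graded-abnormality tables (SAP 7.2.3).* Toxicity grades are assigned to laboratory results only, so ECG intervals do not enter.
3. *Adverse event tables (SAP 7.1.6).* Protocol 7.5 says that "abnormal assessments (e.g., ECG, X-rays, and vital signs) that are associated with signs and/or symptoms must be recorded as an AE" or SAE if the definition is met. Without signs or symptoms that section does not require recording. The adverse event definition in protocol 7.1.1 is broad enough to permit it, and Appendix 3 would supply the grade. Once recorded, the event appears by preferred term and, at Grade 3, in the table of Grade 3 or higher events. This route is open but discretionary.
4. *Further analyses (SAP 7.5).* Optional, with no stated trigger.
5. *By-subject listing (SAP 7.5).* Not a summary, and not stated to contain interval values.

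**Appendix 3 cut-offs applied to hypothetical pairs of readings**

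| Baseline (ms) | Week 12 (ms) | Increase (ms) | Grade by increase | Reaches 450 ms? |
|---|---|---|---|---|
| 385 | 445 | 60 | 3 | No |
| 389 | 449 | 60 | 3 | No |
| 400 | 449 | 49 | 2 | No |

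If both tracings are called normal, each pair is normal to normal in the shift table.

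**Illustrative size in a group of 30**

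Assumptions, none of them from the documents except the 450 ms limit: baseline QTcF normal with mean 410 and SD 20 ms, cut off at 450 ms; change independent of baseline with SD 15 or 20 ms; mean change 0 or 10 ms. The 450 ms limit is the male one (470 ms for females) and applies at Screening, so the truncation is a simplification.

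| Expected number of 30 (SD 15 / SD 20) | Mean change 0 | Mean change 10 ms |
|---|---|---|
| Week 12 QTcF above 450 ms | 1.2 / 2.0 | 2.9 / 3.9 |
| Increase of at least 30 ms | 0.7 / 2.0 | 2.7 / 4.8 |
| of these, still at or below 450 ms | – | 1.6 / 2.4 |

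The second row is 30 × P(Z ≥ (30 − mean)/SD). For example, 30 × P(Z ≥ 1.33) = 2.7 and 30 × P(Z ≥ 1) = 4.8. With a 10 ms mean rise, about half of the subjects with an increase of at least 30 ms would not exceed 450 ms.

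**Precision of a mean change (95% half-width)**

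- Within one group of 30: 2.045 × SD/√30 = 5.6 ms (SD 15) or 7.5 ms (SD 20).
- Group of 30 against Group 2 (n = 10): 2.024 × SD × √(1/30 + 1/10) = 11.1 ms or 14.8 ms.

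A 10 ms shift would stand clear of zero within a group, but a 10 ms difference from the TAF control would not.

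**Can Appendix 3 be programmed literally?** No. Its Grade 1 change criterion counts any increase under 30 ms. With no drug effect half of the subjects rise by chance, so 30 × 0.5 = 15 of 30 would be Grade 1 or higher. Read in milliseconds, the bands also leave gaps, for example absolute 471–479 ms and increases of 51–59 ms.

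**The case against.** A reader might infer that asymptomatic QTc prolongation can reach no summary table at all. The documents do not support that: the adverse event route is open to an investigator who chooses it, and the SAP allows further analyses. Nor is the shift table blind to interval change by design, because protocol 6.8.3 has the reviewer compare intervals with pretreatment. A normal-to-normal miss is possible, but it is not built in.

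A reader might also take the statement that QTc will be reported as a broken commitment. It names a correction formula in a procedures section and in schedule footnotes. Protocol 8.6 bases the safety evaluation on laboratory tests and adverse events and promises no ECG analysis, so the shift table already goes beyond it. SAP 7.7, which declares no deviation from protocol-specified safety analyses, is not contradicted.

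The context also lowers the stakes. Protocol 1.2.3 reports no cardiovascular effect in monkeys at single doses up to 500 mg/kg. The only scheduled on-treatment ECG is at Week 12, on site equipment and not timed to dose, while the parent drug's half-life is about an hour. A mean change from it would be a weak QT assessment.

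These points limit the claim but do not remove it. Discretionary recording and optional analyses are not a pre-specified summary, and the existing table cannot itself show the QTc finding that would prompt a further analysis.

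**Conclusion.** The point holds as a gap in the SAP: no QTcF summary is pre-specified, and asymptomatic prolongation is tabulated under its own name only at an investigator's or analyst's discretion. That follows from the text and does not rest on the assumed QTcF distribution. The assumed figures show only scale: with a 10 ms mean rise, about 1.6 to 2.4 of 30 subjects would have an increase of at least 30 ms without exceeding 450 ms.

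The gain from closing the gap is descriptive. Group means and counts would become visible, but a contrast with Group 2 would be imprecise (half-width 11.1 to 14.8 ms on the same assumptions). The change is worth making because it replaces sole reliance on an unblinded judgement with a variable already measured, at small cost.

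**What to change.** In SAP 7.5 add, by treatment group:

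- QTcF at baseline and Week 12 and change from baseline, as the 8-number summary. SAP Table 3-3 already defines the ECG window and baseline value.
- Number and percentage of subjects by absolute QTcF in contiguous bands: up to 450, above 450 to below 480, 480 to below 500, and at least 500 ms.
- Number and percentage by increase from baseline: below 30, 30 to below 60, and at least 60 ms.

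These use the Appendix 3 Grade 2 and Grade 3 cut-offs, plus 450 ms. Do not apply the literal Grade 1 change criterion. Include QTcF in the by-subject ECG listing, and keep the investigator shift table.

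The cost is one or two tables, provided the interval values are in the clinical database. The documents imply this but do not state it: protocol 9.1.6 says the eCRF captures what the schedule requires, and footnote e to the schedule names QTcF. If the values are not held, the SAP should say so, and the cost becomes data retrieval. A table note should state that the values are single, site-read Week 12 readings not timed to dose, and that comparison with Group 2 is descriptive only.

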## **7.6. Other Safety Measures**

No additional safety measures are specified in the protocol.

## **7.7. Changes From Protocol-Specified Safety Analyses**

There are no deviations from the protocol-specified safety analyses.

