### **8.6.2. Adverse Events**

Clinical and laboratory adverse events (AEs) will be coded using the Medical Dictionary for Regulatory Activities (MedDRA). System Organ Class (SOC), High-Level Group Term (HLGT), High-Level Term (HLT), Preferred Term (PT), and Lower-Level Term (LLT) will be attached to the clinical database.

Summaries (number and percentage of subjects) of treatment-emergent (TE) AEs (by SOC and PT) will be provided by treatment group:

- All TEAEs
- TEAEs of Grade 3 or higher
- TEAEs of Grade 2 or higher
- All TE treatment-related AEs
- TE treatment-related AEs of Grade 3 or higher
- TE treatment-related AEs of Grade 2 or higher
- All TE SAEs
- All TE treatment-related SAEs
- All TEAEs leading to premature discontinuation of any study drug
- All TEAEs leading to temporary interruption of any study drug

All AEs collected during the study will be presented in the data listings.

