#### 7.1.6. Summaries of Adverse Events and Deaths

AEs will be summarized based on the Safety Analysis Set.

3 sets of summaries will be generated: (1) all TEAEs for 12 Week Regimen (2) all TEAEs for 48 Week Regimen (Group 1-3, and 5). (3) all AEs during TFFU period (AEs that occur during TFFU after Week 48) will be listed, and summary tables will be presented using the TFFU Analysis Set as appropriate.

A brief, high-level summary of the number and percentage of subjects who experienced at least 1 TEAE in the categories described below will be provided by treatment group. All deaths observed in the study will also be included in this summary.

The number and percentage of subjects who experienced at least 1 TEAE will be provided and summarized by SOC, PT and treatment group:

- TEAEs (with severity)

For the AE categories described below, summaries will be provided by PT and treatment group:

- TEAEs
- TEAEs of Grade 3 or higher
- TE treatment-related AEs
- GS-9992 only TE treatment-related AEs (Group 1, 3-5)
- TE treatment-related AEs of Grade 3 or higher
- TE SAEs
- TE treatment-related SAEs
- TEAEs leading to premature discontinuation of GS-9992
- TEAEs leading to premature discontinuation of TAF
- TEAEs leading to dose modification or temporary interruption of GS-9992
- TEAEs leading to dose modification or temporary interruption of TAF

Multiple events will be counted only once per subject in each summary. Adverse events will be summarized and listed first in alphabetic order by SOC and then by PT in descending order of total frequency within each SOC. For summaries by severity grade, the most severe grade will be used for those AEs that occurred more than once in an individual subject during the study.

In addition to the by-treatment summaries described above, data listings will be provided for the following AEs:

- All AEs, indicating whether the event is treatment-emergent
- All AEs of Grade 3 or higher
- SAEs
- All deaths
- AEs leading to premature discontinuation of any study drug
- AEs leading to dose modification or temporary interruption of any study drug

For subjects in the TFFU Analysis Set, by-subject listings will be provided as follows:

- All AEs
- AEs of Grade 3 or higher
- All SAEs
- All deaths

The listings will indicate whether an event is treatment-emergent, and whether the event occurred during TFFU.

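### SAP 7.1.6 omits the protocol's two Grade 2-or-higher adverse-event summaries while SAP 7.7 denies any departure, so no treatment-related table separates Grade 2 from Grade 1

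*SAP*

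**What the plan says.** Protocol 8.6.2 sets the level of presentation: "Summaries (number and percentage of subjects) of treatment-emergent (TE) AEs (by SOC and PT) will be provided by treatment group". Its ten categories include "TEAEs of Grade 2 or higher" and "TE treatment-related AEs of Grade 2 or higher", each alongside a Grade 3-or-higher version.

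SAP 7.1.6 specifies one table by system organ class, preferred term and group, "TEAEs (with severity"). It then gives a list of further categories under this instruction: "For the AE categories described below, summaries will be provided by PT and treatment group". The only treatment-related entry on that list with a grade cut is "TE treatment-related AEs of Grade 3 or higher"; the only all-causality entry with one is also at Grade 3. The short overview table is tied to the same categories, so it has no Grade 2 row either.

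On departures from the protocol, SAP 7.7 says "There are no deviations from the protocol-specified safety analyses".

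**The concern.** Safety and tolerability of the 12-week regimens is a primary objective (Protocol Section 2; SAP 1.1). A reader who relies on SAP 7.7 will assume that the adverse-event outputs match the protocol. The SAP does record a change elsewhere (6.4 declares that the pharmacokinetic analysis was dropped), so a statement of no change carries weight.

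What is at stake is the severity breakdown of events attributed to study drug. Protocol 1.2.2 reports that all treatment-emergent events in the earlier GS-9992 Phase 2 study were mild or moderate. If that holds here, a related-event table cut at Grade 3 may be nearly empty, and the all-grade related table would not show how many of its events were worse than mild.

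**Working it through.** **1. Matching the two lists.**

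| Protocol 8.6.2 category | SAP 7.1.6 counterpart |
|---|---|
| All treatment-emergent events | Yes, also with severity |
| Grade 3 or higher | Yes |
| Grade 2 or higher | **None** |
| Treatment-related | Yes, plus an added GS-9992-only version |
| Related, Grade 3 or higher | Yes |
| Related, Grade 2 or higher | **None** |
| Serious | Yes |
| Related serious | Yes |
| Leading to discontinuation | Yes, split by drug |
| Leading to interruption | Yes, split by drug |

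Eight of ten match. The two without a counterpart are exactly the two Grade 2 summaries. No other part of the SAP records the change.

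**2. What can be rebuilt for all causes.** SAP 7.1.6 says "For summaries by severity grade, the most severe grade will be used for those AEs that occurred more than once". On the Grade 1-4 scale, adding the Grade 2, 3 and 4 counts in a row of the severity table gives the Grade 2-or-higher count for that row. The condition matters because SAP 7.1.2 describes two scales, Grade 1 to 4 and mild/moderate/severe, with no mapping between them and no statement of which one the table uses.

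**3. What can be rebuilt for related events.** The tables give related events at all grades (A) and at Grade 3 or higher (C). The most they yield is A − C, the subjects whose worst related grade was 1 or 2 combined (or not recorded). The severity table ignores relatedness, so it does not split that remainder.

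**4. Illustration from Protocol Table 1-4 (subjects with study drug-related events).**

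| | TAF (N = 866) | TDF (N = 432) |
|---|---|---|
| Any grade (A) | 123 | 68 |
| Grade 2-4 (B) | 33 | 21 |
| Grade 3-4 (C) | 6 | 2 |
| A − C, all the SAP's related tables would show below Grade 3 | 123 − 6 = 117 | 68 − 2 = 66 |
| B − C, worst related grade is 2 | 33 − 6 = 27 | 21 − 2 = 19 |
| (B − C)/B | 27/33 = 82% | 19/21 = 90% |

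Without row B, the 27 cannot be separated from the other 90 (123 − 33) within the 117.

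**5. Scale in this trial, on an assumption.** Suppose the TAF rates applied here: p = 33/866 = 3.8% for related Grade 2 or higher and p = 6/866 = 0.7% for related Grade 3 or higher. The chance of at least one such subject in a group of n is 1 − (1 − p)^n.

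| n | Related Grade 2 or higher | Related Grade 3 or higher |
|---|---|---|
| 10 | 32% | 7% |
| 20 | 54% | 13% |
| 30 | 69% | 19% |

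Expected numbers at n = 30 are 30 × 33/866 = 1.1 and 30 × 6/866 = 0.2 subjects. There is no plan figure to reproduce, since the point rests on no sample-size or error-rate calculation.

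**The case against.** The best case for the SAP is that little is hidden. A reader might infer that related Grade 2 events appear in no table and survive only in listings. The documents do not support that. Such events are counted in the all-grade treatment-related table, in the GS-9992-only related table where attributed to that drug, and within the severity table. Every event is also listed by subject, and with planned groups of about 10 to 30 a reader could count them by hand. One of the two omitted summaries is largely covered by the severity table. All of this stands, and it confines the loss to the Grade 1 versus Grade 2 split of related events.

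A reader might also take Grade 2 to be the tier that carries the safety information for GS-9992. That is inference. Protocol 1.2.2 says most earlier events were judged unrelated, and none of the first 15 subjects in the 200 mg cohort had a related event, so a related Grade 2 table could itself be sparse. The earlier study also had Grade 3 ALT elevations. Laboratory abnormalities are usually not recorded as adverse events (Protocol 7.5), and SAP 7.2.3 and 7.2.4 cover them separately.

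Finally, the Table 1-4 figures are subjects, not events. They come from TAF and TDF without GS-9992, through Week 48, so they say nothing about tolerability across the GS-9992 doses.

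None of this answers the two textual facts: the summaries are missing, and the SAP says that nothing changed.

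**Conclusion.** The omission is certain: two of ten protocol-specified summaries are absent from SAP 7.1.6, and the statement in 7.7 is wrong as written. The lost information is small but real. No planned treatment-related table distinguishes Grade 2 from Grade 1. The all-causality Grade 2-or-higher counts are recoverable only if the severity table uses the Grade 1-4 scale, which SAP 7.1.2 leaves open.

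The TAF figures show how such a split can look (27 of 33 at worst Grade 2) and are context only. The chances per group assume that TAF rates carry over, which the documents do not establish. No endpoint or estimate changes, and the study is exploratory and descriptive. This is a minor point, worth correcting because it concerns a primary objective.

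**What to change.** Restore both Grade 2-or-higher categories to the SAP 7.1.6 list, which also brings them into the overview table. Presenting the treatment-related table by Grade 1-4 would serve equally well for the related events. State in 7.1.2 or 7.1.6 that the severity table uses the Grade 1-4 scale.

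Correct 7.7. While doing so, reconcile a second undeclared difference: the protocol asks for every category by system organ class and preferred term, whereas the SAP specifies preferred term alone for all but the severity table. Recording the removal in 7.7 without restoring the tables would make the statement accurate but would not return the breakdown.

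The cost is two extra tables, repeated for each analysis period that 7.1.6 already covers, from grades and causality assessments already collected. If the SAP is final, its introduction already provides for later changes to be documented in the study report.
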